### **5.1.2.1 Asthma worsening or asthma exacerbation preventing OCS down-titration**

The OCS dose titration will be interrupted in case of one of the following circumstances related to the asthma condition:

- Asthma deterioration will be assessed by the investigators when there is an increase in ACQ-6 scores of  $\geq 0.5$  from the value at Visit 2. If the ACQ-6 score at Visit 2 is missing, the 1st score recorded post-Visit 2 and pre-OCS reduction may be used as baseline value for the 0.5-point increase (note, however, that it will not be used to impute the baseline for ACQ-6 analysis). The Investigator will decide whether the worsening of asthma should lead to an interruption in tapering of OCS dose until asthma control improves.
- In case of an asthma exacerbation that requires treatment with systemic corticosteroids for at least 3 consecutive days, hospitalization, or emergency room admission, the OCS dose titration will be interrupted, and appropriate treatment will be administered as described in Section [5.2.3](#).

After recovery from the first asthma deterioration or exacerbation, patients will be offered to continue OCS tapering down at a slower speed (ie, Q4W); however, in the case of a second event of asthma deterioration or exacerbation, the OCS reduction will be stopped.

The lower OCS dose (0 mg or above, if required to control asthma disease) that is not changed during a period of 4 weeks and that ensures a patient does not suffer from an asthma exacerbation or that avoids the occurrence of an asthma deterioration/worsening requiring an increase in OCS dose, based on investigator criteria, will be considered the final OCS dose of the OCS reduction phase, and, thereafter, the patient will initiate the OCS maintenance phase on that OCS dose.

## **5.2 Safety assessments**

### **5.2.1 HPA axis evaluation**

For all patients, HPA axis integrity will be evaluated after 4-weeks on 5 mg/day and prior to tapering down the OCS dose (for patients with baseline OCS doses equal to 5 mg/day, this will be assessed 4 weeks after the first dose of benralizumab administration and before initiation of the OCS reduction phase)

First, a screening method with morning serum cortisol is done (8-9 am morning cortisol level), to evaluate whether the patient has:

- Normal cortisol levels
- Complete adrenal insufficiency (AI)

Cortisol levels from the morning cortisol test that are below normal range and above the Complete AI range are considered “Indeterminate,” and require additional testing described below.

Secondly, the ACTH stimulation test (ie, Synacthen®, Cortrosyn™) is done within approximately 1 week in the subset of patients with indeterminate results from the morning cortisol test [see also Section [5.2.1.2](#) for details]. The ACTH stimulation test is more specific than the morning cortisol test, and can determine whether the patient has:

[figure not shown]
- Normal cortisol levels
- Complete AI
- Partial AI.

The process will be as described in [Figure 2](#).

For females using oral estrogen-containing contraceptives or oral estrogen-containing hormone replacement therapy, the threshold for normal values will be 2 times the normal morning cortisol levels and 1.5 times the normal ACTH stimulation test cortisol levels. Details related to values for normal, partial AI, and complete AI for these patients are provided in the laboratory manual.

For the morning cortisol test, the last OCS dose should be taken  $\geq$  24 hours prior to testing. Additionally, patients must not take ICS (or ICS/LABA if in single inhaler) treatment on the morning of the cortisol testing (for patients taking a once-daily ICS/LABA formulation, e.g. fluticasone furoate/vilanterol patients must not take the treatment  $\leq$  24 hours prior to the morning of the cortisol testing). If a patient requires a short course of macrolides, antivirals, or azoles, there must be a window of  $\geq$ 1 week prior to the testing of cortisol levels (see Section [7.8](#)).

**Figure 2 HPA axis evaluation**

**Figure 2:** For normal cortisol levels with concurrent signs/symptoms of AI, OCS down-titration should continue at a slower pace (1 mg Q4W). For complete AI identified via morning cortisol testing, refer to section 5.2.1.1 for instructions on 3-month repeat testing. For partial AI or complete AI identified via ACTH stimulation test see Section 5.2.1.2 for instructions on 2-month or 3-month repeat testing respectively. Patients who have Partial AI will undergo an additional morning cortisol test (and if required, ACTH stimulation test for indeterminate result) approximately 1-2 weeks prior to the end of the OCS Reduction phase. Patients who have Complete AI or Partial AI at the end of the OCS Reduction Phase, will undergo a final morning cortisol test (and if required, ACTH stimulation test for indeterminate result) approximately 1-2 weeks prior to the end of the Maintenance phase (prior to EOT).

*Note:* Central lab reports list reference ranges that are different than this study-reference ranges. To interpret laboratory results for each morning cortisol or ACTH stimulation test, please look for the study-specific lab alerts indicating normal, partial AI, and complete AI on the lab reports provided by central labs. The study-specific reference ranges for normal, partial AI, and complete AI are provided in the laboratory manual.

### 5.2.1.1 Morning cortisol test (done at “OCS ≤ 5mg/day [morning cortisol]” visit)

For the morning cortisol test, hold OCS dose and other concomitant medications that could interfere with cortisol results per Section 5.2.1. Serum samples for cortisol will be collected between 8 and 9 am and will be sent to a central laboratory for evaluation. Once the results are available, the site will inform the patient of the results via telephone. Depending on the result, the actions that will be implemented are as follows:

- If cortisol levels are within normal range and the patient does not exhibit any signs and/or symptoms of AI, the patient will continue OCS down-titration by 2.5 mg Q4W

- If cortisol levels are within normal range but the patient exhibits signs and/or symptoms of AI, then OCS down-titration should continue at a slower pace (1 mg Q4W).
- If cortisol levels are below the normal range and above the complete AI range (indeterminate result), then the patient will be instructed to maintain the current OCS dose and come back to the site within 1 week for an ACTH stimulation test (Section 5.2.1.2)
- If complete AI is confirmed, sites will inform patients that the OCS dose will remain the same without further reduction until there is evidence of recovery from the complete AI without worsening of asthma control. The morning cortisol test will be repeated 3 months later, and patients will be educated for symptom awareness of adrenal suppression and use of steroid emergency cards. During this repeat test 3 months later, the patient would also repeat all clinical assessments that were done with the initial morning cortisol test (see Table 1). After the repeat morning cortisol test, the site will inform the patient based on the results as follows:
  - If morning cortisol results at 3 months indicate normal cortisol values, then reductions will be 2.5 mg Q4W, and the patient would subsequently move to maintenance phase at OCS 0mg (or lowest possible dose)
  - If morning cortisol tests at 3 months are indeterminate, then reductions will be delayed further, and the patient would return approximately 1-week later for an ACTH stimulation test:
    - If normal result after ACTH stimulation: Reduce by 2.5mg Q4W then move to maintenance phase at 0mg (or lowest possible dose)
    - If the result is Partial AI after ACTH stimulation: Reduce by 1mg Q4W then move to maintenance phase at 0mg (or lowest possible dose)
    - If complete AI result after ACTH stimulation: OCS dose will not be reduced further, move to maintenance phase at current OCS dose
  - If morning cortisol tests again indicate complete AI at 3 months, the OCS dose will not be modified as this is the final attempt. The patient would move to maintenance phase at OCS 5mg (or lowest possible dose).

Patients who have Partial AI will undergo an additional morning cortisol test (and if required, ACTH stimulation test for indeterminate result) approximately 1-2 weeks prior to the end of the OCS Reduction phase. Patients who have Complete AI or Partial AI at the end of the OCS Reduction Phase, will undergo a final morning cortisol test (and if required, ACTH stimulation test for indeterminate result) approximately 1-2 weeks prior to the end of the Maintenance phase (prior to EOT). In the absence of evidence of HPA axis recovery, corticosteroid supplementation is recommended during situations of stress (ie, fractures, surgery, trauma, labor, invasive dental procedures, severe systemic infections, major burns, and fever  $>38.5^{\circ}\text{C}$ ). Additionally, patients with Partial AI or Complete AI at the end of the Maintenance phase should be referred to an endocrinologist or other appropriate specialist, per Investigator discretion.

Details related to values for normal, partial AI and complete AI are provided in the laboratory manual.

### 5.2.1.2 ACTH stimulation test

The ACTH stimulation test (e.g., Synacthen®, CortrosynTM, etc.) test will be performed when morning cortisol levels are below the normal range (but above complete AI levels). Please refer to the package insert of the product used locally for further guidance on preparation and administration. The sites will inform the patients of the morning cortisol results via phone call, and a visit will be scheduled within 1 week for the ACTH stimulation test. In the event of any issues with availability of the product used for the ACTH stimulation test, please consult with AZ study physician for further guidance.

For the ACTH stimulation test, hold OCS dose and other concomitant medications that could interfere with cortisol results per Section 5.2.1. An injection of the fast-acting ACTH stimulant will be given intravenously. Serum samples for cortisol will be collected between 8 and 9 am and will be sent to a central laboratory for evaluation as follows: a blood sample for serum cortisol will be collected at 0 minutes (before injection) and 30 minutes after the injection. Peak cortisol response at 30 minutes will be selected to assess AI, and the OCS taper will follow the applicable scenario below:

- If a normal peak cortisol level is demonstrated at 30 minutes, the site will inform the patient via phone call, and the patient will continue OCS dose titration by 2.5 mg Q4W, and subsequently would move to the maintenance phase at OCS dose of 0mg (or lowest possible dose).
- If the peak cortisol level at 30 minutes is below the normal range yet above the level of complete AI (“partial AI”), or there are some signs/symptoms of AI or corticosteroid withdrawal syndrome, the site will inform the patient to continue OCS down-titration at a slower speed (1 mg Q4W). The morning cortisol test will be repeated 2 months later, as per the process described in [Figure 2](#). During this repeat test 2 months later, the patient would also repeat all clinical assessments that were done with the initial morning cortisol test (see [Table 1](#)).
  - If morning cortisol test results indicate normal cortisol values, then reductions will be up to 2.5 mg Q4W (based on patient’s current OCS dose), and the patient would subsequently move to maintenance phase at OCS 0mg (or lowest possible dose)
  - If morning cortisol test results at 2 months are indeterminate, then reductions will be delayed, and the patient would return approximately 1-week later for an ACTH stimulation test.
    - If normal result after ACTH stimulation: Reduce by 2.5mg Q4W then move to maintenance phase at 0mg (or lowest possible dose)
    - If the result is Partial AI after ACTH stimulation: Reduce by 1mg Q4W then move to maintenance phase at 0mg (or lowest possible dose)

- If complete AI result after ACTH stimulation: OCS dose will not be reduced further, move to maintenance phase at current OCS dose
  - If morning cortisol test results at 2 months indicate complete AI, the OCS dose will not be modified as this is the final attempt. The patient would move to maintenance phase at OCS 5mg (or lowest possible dose).
- If peak cortisol level at 30 minutes indicates complete AI, sites will inform patients that the OCS dose will remain the same without further reduction until there is evidence of recovery from the complete AI without worsening of asthma control. The morning cortisol test will be repeated 3 months later and patients will be educated for symptom awareness of adrenal suppression and use of steroid emergency cards. During this repeat test 3 months later, the patient would also repeat all clinical assessments that were done with the initial morning cortisol test (see [Table 1](#)). After the repeat morning cortisol, the site will inform the patient based on the results as follows:
  - If results indicate normal cortisol values, then reductions will be 2.5 mg Q4W, and the patient would subsequently move to maintenance phase at OCS 0mg (or lowest possible dose)
  - If morning cortisol tests at 3 months indicate indeterminate results, then reductions will be delayed further, and the patient would return approximately 1-week later for an ACTH stimulation test.
    - If normal result after ACTH stimulation: Reduce by 2.5mg Q4W then move to maintenance phase at 0mg (or lowest possible dose)
    - If the result is Partial AI after ACTH stimulation: Reduce by 1mg Q4W then move to maintenance phase at 0mg (or lowest possible dose)
    - If complete AI result after ACTH stimulation: OCS dose will not be reduced further, move to maintenance phase at current OCS dose
  - If morning cortisol tests again indicate complete AI at 3 months, the OCS dose will not be modified as this is the final attempt. The patient would move to maintenance phase at OCS 5mg (or lowest possible dose).

Patients who have Partial AI will undergo an additional morning cortisol test (and if required, ACTH stimulation test for indeterminate result) approximately 1-2 weeks prior to the end of the OCS Reduction phase. Patients who have Complete AI or Partial AI at the end of the OCS Reduction Phase, will undergo a final morning cortisol test (and if required, ACTH stimulation test for indeterminate result) approximately 1-2 weeks prior to the end of the Maintenance phase (prior to EOT).

In the absence of evidence of HPA axis recovery, patients should be instructed to carry some type of identification (worn around the neck or wrist or carried as a card) warning of their clinical status of corticosteroid dependence along with a medical report detailing the treatment measures needed, including intramuscular hydrocortisone requirements. Corticosteroid supplementation is recommended during situations of stress (ie, fractures, surgery, trauma,

labor, invasive dental procedures, severe systemic infections, major burns, and fever  $>38.5^{\circ}\text{C}$ ). Additionally, patients with Partial AI or Complete AI at the end of the study should be referred to an endocrinologist or other appropriate specialist, per Investigator discretion.

Details related to values for normal, partial AI and complete AI are provided in the laboratory manual.

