#### **4.2.3 Maintenance phase**

A patient will enter the approximately 24- to 32-week maintenance phase when they reach an OCS dose of 0 mg/day (or lowest OCS dose possible in case no further OCS down-titration is allowed because of the presence of AI as measured by cortisol levels or in case of inadequate asthma control) without losing asthma control. This could be earlier if OCS dose reduction fails due to clinical deterioration or if the patient experiences an asthma exacerbation. The duration of the maintenance phase will depend on when the patient enters the maintenance phase relative to the dosing cycle of benralizumab. During this phase, patients will continue benralizumab Q8W for 3 doses and then the EOT visit will be scheduled 8 weeks ( $\pm$  7 days) after the last dose of benralizumab (assessments performed as per [Table 1](#)). However, if during this period, the patient experiences asthma deterioration or an exacerbation, the length of the maintenance phase will not be extended and the patient will continue on 3 doses of benralizumab Q8W. Additionally increases in the maintenance OCS dose due to an asthma exacerbation is permitted per investigator discretion. Patients who experience an asthma exacerbation that requires evaluation in an urgent care center or emergency department, hospitalization, or temporary increase of systemic steroids (bolus/burst dosing) will be managed as per details in Section [5.2.3](#).

Patients who have Complete AI or Partial AI at the end of the OCS Reduction phase, will undergo a final morning cortisol test (and if required, ACTH stimulation test for indeterminate result) approximately 1-2 weeks prior to end of the OCS Maintenance phase (prior to EOT visit).

Patients will return the ePRO at the EOT visit. Completion of the treatment will be registered in IWRs/IVRs at the EOT visit for each patient. After stopping study drug, the patient will be adjusted to a post-study asthma maintenance regimen (which may include a respiratory biologic, if needed), per Investigator discretion.

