**Table 2 OCS down-titration approaches**

Initial OCS dose/day	OCS down-titration to reach an OCS dose of:				
	20 mg	10 mg	7.5 mg	5 mg	0 mg
>20 mg	Reduction of 5 mg weekly until reaching dose of 20 mg/day	Reduction of 5 mg Q2W until reaching dose of 10 mg/day	2.5 mg Q2W until reaching dose of 7.5 mg/day	2.5 mg Q4W until reaching dose of 5 mg/day	No AI: reductions of 2.5 mg Q4W until reaching dose of 0 mg/day Risk AI: reductions of 1 mg Q4W and repeat test 2 months later a Complete AI: No OCS dose reduction and repeat test 3 months later b
>10 mg to ≤20 mg		Reduction of 5 mg Q2W until reaching dose of 10 mg/day	2.5 mg Q2W until reaching dose of 7.5 mg/day	2.5 mg Q4W until reaching dose of 5 mg/day	No AI: reductions of 2.5 mg Q4W until reaching dose of 0 mg/day Risk AI: reductions of 1 mg Q4W and repeat test 2 months later a Complete AI: No OCS dose reduction and repeat test 3 months later b
>7.5 mg to ≤10 mg			2.5 mg Q2W until reaching dose of 7.5 mg/day	2.5 mg Q4W until reaching dose of 5 mg/day	No AI: reductions of 2.5 mg Q4W until reaching dose of 0 mg/day Risk AI: reductions of 1 mg Q4W and repeat test 2 months later a Complete AI: No OCS dose reduction and repeat test 3 months later b
>5 mg to ≤7.5 mg				2.5 mg Q4W until reaching dose of 5 mg/day	No AI: reductions of 2.5 mg Q4W until reaching dose of 0 mg/day Risk AI: reductions of 1 mg Q4W and repeat test 2 months later a Complete AI: No OCS dose reduction and repeat test 3 months later b
5 mg					No AI: reductions of 2.5 mg Q4W until reaching dose of 0 mg/day Risk AI: reductions of 1 mg Q4W and repeat test 2 months later a Complete AI: No OCS dose reduction and repeat test 3 months later b

a Risk AI means “partial AI” cortisol testing confirmed with ACTH stimulation testing. After repetition of the test 2 months later, the decision to further reduce OCS dose will be based on the morning cortisol test results. If test results are normal, the OCS dose may be reduced directly to 0 mg/day (if patient is receiving ≤3 mg); the patient will continue receiving 1 mg Q4W if still at risk. If complete AI is indicated, OCS dose will not be modified.

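### Protocol 5.2.1.2 names 5 mg as the maintenance dose after complete AI at the 2-month repeat, although the branch's own taper normally leaves patients at about 3 mg and the rest of the plan keeps the current dose

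*Protocol*

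**What the plan says.** HPA testing starts after 4 weeks on 5 mg/day (Protocol 5.2.1). If the ACTH stimulation test shows partial AI, "the site will inform the patient to continue OCS down-titration at a slower speed (1 mg Q4W" per step), and morning cortisol is repeated 2 months later (Protocol 5.2.1.2). Three outcomes of that repeat matter here:

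- **Complete AI on morning cortisol.** "If morning cortisol test results at 2 months indicate complete AI, the OCS dose will not be modified as this is the final attempt". The next sentence reads "The patient would move to maintenance phase at OCS 5mg (or lowest possible dose").
- **Indeterminate morning cortisol, then complete AI on the ACTH test.** "OCS dose will not be reduced further, move to maintenance phase at current OCS dose".
- **Normal result.** Table 2 footnote a says that "the OCS dose may be reduced directly to 0 mg/day (if patient is receiving ≤3 mg"), so the plan expects some patients to be at 3 mg or less at this visit.

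For complete AI at the 2-month repeat, Table 2 footnote a adds "If complete AI is indicated, OCS dose will not be modified". The SAP reproduces that footnote in its own Table 2. Footnote a of Protocol Table 3, which covers the same repeat after recovery from an asthma event, has no such sentence.

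The sentence naming 5 mg also closes the 3-month branches in 5.2.1.1 and 5.2.1.2, which open with "If morning cortisol tests again indicate complete AI at 3 months, the OCS dose will not be modified as this is the final attempt". In those branches the dose has been held since the initial test.

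**The concern.** The two sentences of the 2-month bullet cannot both describe a patient who has tapered to 3 mg: the dose is left alone, yet the patient enters maintenance at 5 mg. This is an operative dosing instruction, and the figure it names fits the held-dose branches rather than this one.

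A site that acted on the figure would raise the dose. Protocol 5.1.1 allows no reduction after the reduction phase, so the higher dose would continue through maintenance. SAP 3.1 takes the final reduction-phase dose from the investigator's entry, provided that it was held for 4 weeks without worsening. A 5 mg entry could therefore reach the supportive dose-reduction outcomes. SAP 4.2.7.1 plans plots for patients who go from partial AI to complete AI at the repeat, so the sponsor foresees the pathway.

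**Working it through.** **1. The named figure.** In the 3-month branches no reduction is made before the repeat: 5 − 0 = 5 mg. The figure is reproduced there.

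**2. The dose in the 2-month branch.** Dose at repeat = 5 − (number of 1 mg steps taken by then). The documents do not fix the exact timing, so these are assumptions:

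- repeat at 8 or 8.7 weeks;
- first step 0, 1 or 4 weeks after the ACTH result;
- a step due on the test day taken or not.

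That gives 2 × 3 × 2 = 12 variants. The dose is 3 mg in 8, 2 mg in 3, 4 mg in 1 and 5 mg in none. The range of 2 to 4 mg assumes an uninterrupted taper. A taper held or stepped up for an exacerbation or deterioration (Protocol 4.2.2, 5.2.3) can leave the patient at up to 5 mg.

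**3. Extra exposure if a site followed the figure.** Rise = 5 − 4, 5 − 3 or 5 − 2, which is 1, 2 or 3 mg/day. Maintenance of 24 to 32 weeks is 168 to 224 days.

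- 1 mg/day: 168 to 224 mg
- 2 mg/day: 336 to 448 mg
- 3 mg/day: 504 to 672 mg

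**4. Percentage categories.** Reduction = (b − f)/b for baseline b and final dose f, so a threshold T is met when b ≥ f/(1 − T). For a 3 mg patient recorded at 5 mg:

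| Category | Met at f = 5 mg if b is | Met at f = 3 mg if b is | Lost when b is |
|---|---|---|---|
| >0% | >5 mg | ≥5 mg | 5 mg |
| ≥50% | ≥10 mg | ≥6 mg | 6 to <10 mg |
| ≥75% | ≥20 mg | ≥12 mg | 12 to <20 mg |
| ≥90% | ≥50 mg | ≥30 mg | 30 to <50 mg |

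Examples: at b = 7.5 mg, (7.5 − 3)/7.5 = 60% against (7.5 − 5)/7.5 = 33%. At b = 12.5 mg, 76% against 60%. No category changes for b above 5 to <6, 10 to <12, or 20 to <30 mg. With f = 4 mg the affected baselines narrow to 5, 8 to <10, 16 to <20 and 40 to <50 mg. With f = 2 mg some category changes at every baseline from 5 to <50 mg.

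**5. Endpoints that do not move.** Neither 3 nor 5 mg is 0 mg, so the first primary endpoint is unchanged. Both are ≤5 mg with AI as the reason for stopping, so the second primary endpoint is unchanged. The ≤5 mg supportive endpoint is unchanged for the same reason.

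**6. Weight of one patient.** 1/600 = 0.17 percentage points on an overall supportive proportion, at most.

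**The case against.** The strongest reply is that the text already resolves itself. The bullet opens by leaving the dose alone, and its bracket offers the lowest possible dose. Protocol 4.2.3 describes entry to maintenance at the "lowest OCS dose possible in case no further OCS down-titration is allowed because of the presence of AI as measured by cortisol levels". Protocol 5.1.2.1 starts maintenance on the lower dose left unchanged over 4 weeks without exacerbation or deterioration, and SAP 3.1 defines the final dose in similar terms. A site would have to pass over all of this. SAP 2.2.1 also counts problems with titration below 5 mg/day as important deviations, and SAP 4.2.5.1 lists end dose and reason for every patient not reaching 100% reduction.

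Most of this stands, and it is why the text cannot be read as ordering an increase. It does not remove the inconsistency. The bracket is a second alternative with no rule for choosing it. Elsewhere in the same section it follows a 0 mg target, where it can only mean a dose at or above the named figure. A site that followed the printed figure would not obviously be recorded as deviating.

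A reader might also think that Table 3 settles the matter, because its 0 mg column says no reduction with complete AI. That entry carries a 3-month repeat, so it covers the initial test. The footnote that covers the 2-month repeat is silent on complete AI.

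**Conclusion.** The bullet is inconsistent as written, and the point is minor. The opening sentence, Table 2 footnote a, the ACTH sub-bullet, Protocol 5.1.2.1 and SAP 3.1 all lead to the current dose; only the named figure departs from it.

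The documents do not support two stronger inferences. One is that the protocol mandates a rise to 5 mg: the text just listed says otherwise. The other is that 5 mg would harm the patient: Protocol 1.1 treats about 5 mg/day of prednisone as the physiological dose, and nothing in the documents shows harm from that level in complete AI. That the figure was carried over from the 3-month branches is a plausible inference from the matching wording, not a documented fact.

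The size is conditional on a site following the figure: 1 to 3 mg/day (usually 2) for 24 to 32 weeks, a smaller mg reduction, and at some baselines the loss of a supportive category. For a patient still at 5 mg after an interrupted taper, nothing changes. The number of patients in this branch is not given and is not estimated here.

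**What to change.** Make two wording changes in the protocol:

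1. In the 2-month complete-AI bullet of 5.2.1.2, replace the 5 mg figure and its bracket with: current OCS dose. This matches the ACTH sub-bullet and remains correct for a patient still on 5 mg. The 3-month bullets can stay.
2. Add to Table 3 footnote a the sentence already in Table 2 footnote a: "If complete AI is indicated, OCS dose will not be modified".

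The SAP, data collection and sample size need no change. Protocol 10.5 requires a new version and ethics committee approval for substantial changes, so both edits are best carried with the next amendment, or sent as a site clarification if judged not substantial.
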